REIMS	Rapid Evaporative Ionisation Mass spectrometry
DESI	Desorption Electrospray Ionization
DWI	Diffusion weighted image

KEYWORDS

Innovations
Endometrial
Cancer
3D
Ultrasound
Radiomics

STUDY SUMMARY

TITLE Effectiveness of advanced diagnostic tools in women with endometrial cancer: A prospective cohort study

DESIGN Prospective

AIMS (1) Determine the performance characteristics of ultrasound-guided biopsy (using fine forceps e.g. Bettocchi forceps) in the detection of endometrial malignancy and hyperplasia.

(2) Assess the diagnostic accuracy of 3D USS, compared to MRI and final histology with respect to myometrial invasion of endometrial cancer.

(3) Determine whether pelvic imaging (USS pelvis, MRI pelvis and MR spectroscopy) using radiomics can predict grade and type of tumour and prognosis.

(4) Determine if REIMS can diagnose cancer and normal tissue from womb biopsy samples and lymph glands

OUTCOME MEASURES Primary outcome measures:
(1) Histological diagnosis of ultrasound guided biopsy compared to routine care (hysteroscopy guided biopsy). Diagnostic ability (sensitivity, specificity, NPV, PPV) will be compared to gold standard.
(2) Accuracy of diagnosing myometrial invasion in 3D USS compared to MRI
(3) Comparison of radiomics model against standard histological diagnosis in the determination of grade and type of tumour.

Secondary outcome measures:

(1) Patient satisfaction (visual analogue score) of USS guided biopsy
(2) Comparison of accuracy of diagnosis of grade and type of tumour using MR spectroscopy compared to gold standard histopathology
(3) Diagnosis of endometrial cancer and hyperplasia (pre-cancer) in endometrial biopsy samples, and diagnose lymph node metastasis (spread of cancer to

lymph glands), using REIMS, compared with standard histology. Comparison of mass spectroscopy findings of lymph nodes with the primary tumour (the womb cancer)

POPULATION 500 women referred to rapid access clinic with postmenopausal bleeding or intermenstrual bleeding. An additional 100 women will be recruited who were referred to Imperial college following a diagnosis of cancer in other hospitals.

ELIGIBILITY All women presenting to rapid access gynaecology clinic with postmenopausal bleeding or intermenstrual bleeding

EXCLUSION Anyone lacking capacity. <18years old. Pregnant. Any contra-indication carry out a biopsy

DURATION 8 years

1. INTRODUCTION

1.1 BACKGROUND

Endometrial cancer is a tumour originating in the endometrium (womb lining); it is the most common gynaecological cancer in the UK. In 2012, there were almost 100,000 new cases diagnosed in Europe. The lifetime risk of developing endometrial cancer is 1.7%-2.6%. Endometrial cancer classically presents with postmenopausal bleeding (bleeding after the menopause), or intermenstrual bleeding (bleeding imbetween periods).

Although routine management for these women does vary, in general a screening test is performed, typically a pelvic (internal) ultrasound to assess the endometrium (womb lining). A thin and regular endometrial line is associated with a very low risk of endometrial cancer. The pre-test probability of endometrial cancer in women presenting with postmenopausal bleeding is approximately 10%, but this increases with age and other risk factors [Gredmark]. In cases where the endometrial thickness is above the threshold for investigation an endometrial biopsy (sampling cells from the womb lining) is indicated. The biopsy can be taken blindly or under scan or hysteroscopic guidance. Hysteroscopy, the insertion of a small camera into the womb to visualise the womb lining allows direct visualization of the cavity.

In theory an ultrasound-guided biopsy using a very fine forceps (such as Bettocchi) could be used instead of hysteroscopy- guided biopsies of the endometrium. In the literature, only case reports exist; showing its use in the context of investigations for postmenopausal bleeding in women with cervical stenosis [Hammoud]. The technique of ultrasound-guided biopsy is ubiquitous when used elsewhere in the body. It is frequently used to provide histological diagnosis of pelvic masses, (presumed ovarian origin), both abdominally (scanning of the tummy) and transvaginally (internally). Potentially ultrasound guided biopsies could be used as a cheaper, faster and less painful alternative to a hysteroscopy directed biopsies. This technique has not been evaluated before in endometrial cancer.

Once the endometrial biopsy is performed, it is sent to the histologist for further examination. Histological analysis may take several days and patients are either brought back to clinic for discussion of the results or are given a telephone appointment. The patient often will not know the result of the test for up to 2 weeks; thus causing a lot of unnecessary anxiety and distress. Novel diagnostic tests, such as rapid evaporative ionization mass spectrometry (REIMS) may enable real time point of care diagnosis for the first time.

REIMS technique uses standard electrosurgical methods to convert tissue constituents into gas-phase ionic species amenable to mass spectroscopy [Balog, Schafer]. The coupling of electrosurgical dissection with REIMS technology has been coined the iKnife or ‘intelligent surgical device’; and it enables near-real-time characterisation of human tissues *in vivo*. It uses a combination of principal component analysis (PCA) and linear discriminant analysis (LDA) to translate spectral data into more relevant clinical information. Studies have shown that all human tissues have distinctive phospholipid characteristics; and it is these that are interrogated by mass spectroscopy (MS) to provide a tissue signature [Balog]. The surgical aerosol produced by tissue ablation harbours a plethora of information that is not currently used, but could be used to help intra-operative decision-making and diagnoses. Ex-vivo studies have demonstrated clear identification of major tissue types; lung, colon and liver [Balog]. Furthermore, it has been used *in vivo* to identify intestinal cancer, polyps and the origin of metastatic lesions [Balog]. Unpublished data by [name] and [name]’s

group have shown that REIMS technology can distinguish between normal, benign, borderline and malignant ovarian masses with nearly 100% diagnostic accuracy [Phelps]. Part of this research project is to evaluate this new technology in endometrial cancer; in particular to assess if REIMS can diagnose cancer and pre-cancer from biopsies taken in clinic to allow a true one stop diagnosis.

In desorptive electrospray ionisation (DESI) samples of histological slides are taken and imaged pixel-by-pixel; producing mass spectra for each pixel ([name]). It can therefore provide topographically localized biochemical information to supplement standard histopathological classification systems.

Once a diagnosis of cancer is confirmed on biopsy, women get staged to assess the level of spread. Current gold standard is an MRI. A large proportion of women, however, are unable to undergo or complete an MRI scan due to their morbid obesity or claustrophobia. To this end, many have assessed the role of ultrasound in staging endometrial cancer as a cheaper and easier alternative to an MRI. In the last 20 years there has been a rise in the use of 3D ultrasound as it has become commercially available. There is, however a paucity of data on the role of 3D ultrasound in the assessment of myometrial invasion. This research project will assess whether 3D ultrasound is a safe, effective alternative to MRI to assess the depth of spread of womb cancer.

Lastly, the use of radiomics, which is the analysis of vast amounts of quantitative information from imaging, is an emerging technology, used to provide predictive models. The idea being that images of MRIs and Ultrasound from women with known endometrial cancer can be used to develop models which can accurately predict type of tumour and prognosis. This has been applied in a number of cancers such as prostate and lung but not for endometrial cancer.

1.2 RATIONALE FOR CURRENT STUDY

This study will assess the application of new technologies such as ultrasound-guided biopsies, 3D ultrasound and Rapid evaporative ionization mass spectrometry (REIMS) in women with suspected endometrial cancer. These technologies may offer more effective and/or cheaper alternative methods to assess women with suspected cancer. If successful, these technologies can be used in the rapid access gynaecology clinic to provide point of care diagnosis of endometrial cancer from an endometrial biopsy (using REIMS) and accurate assessment of lymph node involvement to help intra-operative decision-making.

2. STUDY OBJECTIVES

Objectives:

- (1) Determine the performance characteristics of ultrasound-guided biopsy (using fine forceps e.g. Bettochi forceps) in the detection of endometrial malignancy and hyperplasia.
- (2) Assess the diagnostic accuracy of 3D USS, compared to MRI and final histology with respect to myometrial invasion of endometrial cancer.
- (3) Determine whether pelvic imaging (USS pelvis, MRI pelvis and MR spectroscopy) using radiomics can predict grade and type of tumour and prognosis.
- (4) Determine if REIMS can diagnose cancer and normal tissue from womb biopsy samples and lymph glands

3. STUDY DESIGN

Prospective cohort study

Setting: Imperial College NHS Trust Hospitals, London

Participants: 500 women referred to rapid access clinic with postmenopausal bleeding or intermenstrual bleeding. An additional 100 women will be recruited who were referred to Imperial college following a diagnosis of cancer in other hospitals.

Duration: 3 years

3.1 STUDY OUTCOME MEASURES

Primary outcome measures:

- (1) Histological diagnosis of ultrasound guided biopsy compared to routine care (hysteroscopy guided biopsy). Diagnostic ability (sensitivity, specificity, NPV, PPV) will be compared to gold standard.
- (2) Accuracy of diagnosing myometrial invasion in 3D USS compared to MRI
- (3) Comparison of radiomics model against standard histological diagnosis in the determination of grade and type of tumour.

Secondary outcome measures:

- (1) Patient satisfaction (visual analogue score) of USS guided biopsy
- (2) Comparison of accuracy of diagnosis of grade and type of tumour using MR spectroscopy compared to gold standard histopathology
- (3) Diagnosis of endometrial cancer and hyperplasia (pre-cancer) in endometrial biopsy samples, and diagnose lymph node metastasis (spread of cancer to lymph glands) using REIMS, compared with standard histology. Comparison of mass spectroscopy findings of lymph nodes with the primary tumour (the womb cancer)

3.1 MAIN STUDY

PART 1: PRE-DIAGNOSIS OF CANCER

All women presenting to the rapid access clinic with postmenopausal bleeding (PMB) and intermenstrual bleeding (IMB) will be approached for consent for inclusion into this study (group A). When women normally attend this clinic the doctor will discuss what will happen - this includes an internal (pelvic scan) and an examination. If the womb lining is thickened on the scan the patient will need a tissue biopsy (this is not that common, most women only need a scan), this will be taken at the same time as the examination in clinic. The device used to take the tissue biopsy is called a pipelle. Only if the patient still needs a biopsy but the patient can't tolerate the examination, or the sample is insufficient or focal (in a small area of the womb as opposed to generalised) then the patient will need to have a hysteroscopy. Hysteroscopy is a procedure in which a hysteroscope; a small camera, is inserted into the womb under local or general anaesthetic. If a patient needs hysteroscopy this will occur at a different appointment.

In this study, all women in group A will be approached for enrolment into the study. Patients will be identified in the gynaecology clinic in Imperial NHS trust (where patients with post menopausal bleeding and suspected cancer get referred). Patients will be identified by the clinical consultants (who are also research supervisors) and clinical research fellow. Patient medical notes will not be used prior to clinic to identify patients, instead the patients will be selected as they attend clinic. At the point of consent, patients will be de-identified given a trial number and anonymised.

Prior to any imaging or examination women will be told what the research involves and if they are happy to proceed. They can consent to all or part of the study. The extra elements of the study include: a 3D ultrasound (not just standard 2D), a second pipelle biopsy sample (only if patients actually would have needed a pipelle anyway) and ultrasound guided biopsy (again only if patients actually would have needed a hysteroscopy guided biopsy). Each will now be discussed in more detail.

All women (group A) will receive a pelvic (internal) ultrasound as per routine care. In addition to the normal 2D ultrasound, women will receive a 3D ultrasound and images will be saved. This adds an additional 1-2 minutes scan time. Depending on the clinician it is sometimes performed as part of routine care.

If the endometrium (womb lining) is thickened >4mm on ultrasound they will require an endometrial biopsy. Usually this will be a pipelle. If the patient is agreeable a second endometrial sample will be taken specifically for research. The histology of first sample will be analysed by conventional pathology and the second sample will be analysed by the new technology REIMS/DESI. REIMS is Rapid Evaporative Ionization Mass Spectrometry and DESI is Desorption Electrospray Ionization. Both are new technologies that use mass spectrometry to analyse chemical composition, and in this case tissue composition. REIMS has been dubbed the 'iKnife' or 'intelligent knife' colloquially as when coupled with surgical diathermy the gas pattern produced is unique to the tissue and helps surgeons know where to cut. The diagnostic ability of this new technology will be compared against the gold standard, which is histological examination.

In cases where the pipelle biopsy cannot be performed in clinic due to poor tolerance, insufficient material or focal lesions a hysteroscopy guided biopsy will be required (local or GA). In this case, the patients will be offered an ultrasound (USS) guided biopsy in the first instance, this will be performed at the same time in clinic. The biopsy will be taken under scan guidance using a very fine forceps such as Bettochi forceps. These forceps are used routinely during hysteroscopy so whilst the instruments are common the application is novel. The biopsy results of this will be sent for standard histology. If the results are inadequate patients will be sent for standard hysteroscopy and biopsy. Patients will also be asked to assess tolerability of the procedure using a visual analogue score.

The tissue generated from the study will be stored in a tissue bank subcollection in a locked and secure freezer in the Institute of Reproductive and developmental biology building on the Hammersmith Hospital site. The sample labels will be coded in order to maintain confidentiality and only authorized members of the research team will have access to the samples. At the end of the research period the tissue samples will be kept for up to 10 years. They would remain securely stored and may be used in subsequent research. It is hoped that the tissue could be used to validate any biomarkers that arise from the study using a combination of immunohistochemical, epigenetics, protein and gene expression analysis. Any data generated from tissue analysis will be stored on Imperial College computers and will be accessed only by members of the research team directly involved in the project.

PART 2: AFTER DIAGNOSIS OF CANCER

In those women with confirmed cancer on histology (subgroup B) - an MRI is performed to assess stage of cancer (current routine standard of care). This will include T1, T2, DWI and contrast enhanced sequences. Patients referred to Hammersmith Hospital from other trusts who are diagnosed with endometrial cancer will be approached for consent and enrolment into latter part of study. These patients will have had an MRI but may not have had all the sequences needed and may therefore require a further MRI scan with additional sequences. MR spectroscopy will be performed on a subset of patients with confirmed cancer (20 patients).

Definitive management of endometrial cancer includes a hysterectomy and the surgical specimen will be examined for depth of myometrial invasion. In the meantime, the saved 3D images from the rapid access clinic will be analysed and rendered to predict the stage of the endometrial cancer. The results of 3D ultrasound, and MRI will be compared against the stage found on the gold standard test (on histological examination).

In women with confirmed endometrial cancer who later go on to require lymphadenectomy as part of standard care (e.g. advanced stage, type 2 tumours or high grade) following MDT discussion will have their lymph nodes examined ex-vivo using REIMS/iKnife/DESI in addition to the gold standard histopathological examination. The diagnostic capabilities of this new technology to identify cancerous lymph nodes will be compared to standard histopathological diagnosis. If this technology is accurate at diagnosing involved lymph nodes it could be used in vivo to enhance intra-operative decision-making. In addition to build the data for endometrial tissue, women receiving surgery will also be consented for an additional endometrial biopsy (under GA or as an ex-vivo sample).

FOLLOW UP:

Following surgery patients will continue with routine standard of care and follow up. Patients will be followed up for 5 years to provide 5-year survival data. Images from ultrasound, MRI pelvis and MR spectroscopy will be analysed to see if they can predict the 5-year survival.

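### Primary outcome 1 promises sensitivity and NPV for ultrasound-guided biopsy, but in the visible text no adequate benign result has a planned reference test, so neither can be estimated

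*Combined protocol and SAP*

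**What the plan says.** Section 3.1 Study outcome measures, primary outcome 1, compares the histological diagnosis from ultrasound-guided biopsy with routine care, meaning hysteroscopy-guided biopsy, and adds: "Diagnostic ability (sensitivity, specificity, NPV, PPV) will be compared to gold standard". It does not define the gold standard for this outcome. Section 3.1 Main study defines one for the mass-spectrometry test: "The diagnostic ability of this new technology will be compared against the gold standard, which is histological examination".

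The same section gives the pathway. Women in whom a pipelle sample is not tolerated, is insufficient, or would not suit a focal lesion are offered ultrasound-guided biopsy before hysteroscopy, and that sample goes to standard histology. Then: "If the results are inadequate patients will be sent for standard hysteroscopy and biopsy".

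For women with cancer, "Definitive management of endometrial cancer includes a hysterectomy and the surgical specimen will be examined for depth of myometrial invasion". On follow-up: "Following surgery patients will continue with routine standard of care and follow up". Section 6 repeats this and defines the end of trial by the last patient's surgery and five years of follow-up.

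Three other statements bear on the point. Participation can be partial: "They can consent to all or part of the study". On identity, "At the point of consent, patients will be de-identified given a trial number and anonymised", whereas for stored tissue "The sample labels will be coded in order to maintain confidentiality". Section 7 expects 80 women to need hysteroscopy and puts the clinic-wide cancer rate at about 10%. It gives no rule for unverified or inadequate results.

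**The concern.** Sensitivity and NPV both need a count of women with disease whose index biopsy was benign. The planned route to hysteroscopy is an inadequate sample, so the comparator is obtained where the index test gave no usable answer. Histology cannot serve as the gold standard here as it does for mass spectrometry, because the ultrasound-guided sample is itself read by histology and would be checked against itself.

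Section 1.1 puts the technique forward as a possible alternative to hysteroscopy-directed biopsy. For a replacement test, the quantity that matters is cancers missed after an adequate benign sample. If the plan collects no data on these, the reported figures depend on how someone later decides to score unverified and inadequate results. A sensitivity near 100% could then be a product of the design and be taken as support for replacement.

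**Working it through.** **Possible references for an adequate benign result**

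- Hysteroscopy: planned after an inadequate result.
- Earlier pipelle: these women are selected because it failed, was insufficient or did not suit a focal lesion.
- Hysterectomy: described for endometrial cancer.
- Five-year follow-up: described after surgery, for survival.
- Additional endometrial biopsy in Section 3.1 Main study: for women having surgery, to build the tissue data.
- Appendix 1 chart: not shown.

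None supplies a reference. In the visible text, no woman is planned to have both an adequate index result and hysteroscopy.

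**The plan's figure.** The 80 cannot be re-derived: 80/500 = 16% and 80/600 = 13.3%, and neither rate is stated. It is taken as given.

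**Identification.** Suppose 80 adequate biopsies give 8 confirmed positives and 72 unverified benign results. Sensitivity = 8/(8 + FN) and NPV = (72 − FN)/72. The same data fit FN = 0 (100%, 100%), FN = 2 (80%, 97.2%), FN = 4 (66.7%, 94.4%) and FN = 8 (50%, 88.9%). With FN free from 0 to 72, sensitivity lies anywhere from 10% to 100% and NPV from 0% to 100%.

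**Effect of the unstated scoring rule.** Inputs from Section 7: 80 women and 10% cancer, so 8 cancers (applying the clinic-wide rate to this subgroup is an assumption). Further assumptions: all 80 accept; 85% of samples are adequate; hysteroscopy finds every cancer after an inadequate sample; there are no false positives; true sensitivity in adequate samples is 60/80/90%.

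- Adequate: 6.8 cancers, 61.2 benign. Inadequate: 1.2 cancers, 10.8 benign.
- TP = 6.8 × sensitivity = 4.08/5.44/6.12. FN among adequate samples = 2.72/1.36/0.68.
- Unverified adequate negatives = 61.2 + FN = 63.9/62.6/61.9, or 79.9/78.2/77.3% of 80.

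| Rule | Sensitivity reads | True | NPV reads | True |
|---|---|---|---|---|
| A: unverified = benign; inadequate excluded | 100% | 60/80/90% | 100% | 95.7/97.8/98.9% |
| B: unverified = benign; inadequate = negative | 77.3/81.9/83.6% | 51.0/68.0/76.5% | 98.4% | 94.8/96.6/97.5% |
| C: verified women only; inadequate = negative | 77.3/81.9/83.6% | 51.0/68.0/76.5% | 90.0% | 94.8/96.6/97.5% |
| D: verified women only; inadequate excluded | 100% | 60/80/90% | 0/0 | 95.7/97.8/98.9% |

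Formulas: A true NPV = 61.2/(61.2 + FN). B sensitivity = TP/(TP + 1.2), against TP/8. B NPV = (72 + FN)/(72 + FN + 1.2), against 72/(72 + FN + 1.2). C NPV = 10.8/12.

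**Ranges at 80% sensitivity.** Under Rule B, 70% adequate gives 4.48/6.88 = 65% against 56%, and 95% adequate gives 6.08/6.48 = 94% against 76%. Under Rule C, a 5% cancer rate gives NPV 11.4/12 = 95% against 98.3%, and a 20% rate gives 9.6/12 = 80% against 92.6%.

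**Specificity.** With a true value of 99% or 95% in adequate samples, FP = 61.2 × 0.01 = 0.612 or 61.2 × 0.05 = 3.06. Rules A and B err by at most 0.04 or 0.21 percentage points. Rule C reads 10.8/(10.8 + FP) = 94.6% or 77.9%, against (72 − FP)/72 = 99.2% or 95.8%.

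**Precision if every woman were verified (exact 95% intervals).** At 50/75/100% uptake (40/60/80 women; 4/6/8 cancers), with every cancer detected, the sensitivity interval starts at 40/54/63%. A yield of 85% has intervals of 70-94%, 73-93% and 75-92%. A PPV of 5/5 has 48-100%.

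**The case against.** The strongest objection is that the Appendix 1 chart, captioned as a summary of routine and trial investigations, is where a retained hysteroscopy step would appear, and it cannot be seen. Section 3.1 Main study also lists ultrasound-guided biopsy among the extra elements of the study and never says that hysteroscopy follows only an inadequate result. With the comparator named in outcome 1, this could be read as index test first and hysteroscopy kept for everyone. That reading is possible but sits badly with the conditional sentence on inadequate results. If it is what the sponsor intends, the text still has to say so.

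Some false negatives are observed if inadequate samples count as negative (1.2 in the illustration), and bounds can always be given. Both are true. Neither identifies sensitivity or NPV, because misses among adequate samples stay unseen. The word inadequate is also undefined. If it covers some benign results from focal lesions, fewer women are unverified.

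The sizes rest on assumed adequacy, sensitivity and scoring rules, and the 80 women are a selected group to whom the 10% rate may not apply. At this sample size the Rule A bias also lies within sampling error: 62/62 to 64/64 has exact lower limits of 94.2-94.4%, which cover the assumed true NPVs. This limits what the figures show. It does not rescue the estimate, because Rule A reads 100% whatever the truth, and recruiting more women would not change that.

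**Conclusion.** The concern holds. As written, the first primary outcome promises two quantities that the described pathway cannot estimate, and following the plan would give values set by an unstated scoring rule. Under the stated assumptions, about 77-80% of the 80 women would have an unverified adequate negative result, hiding 2.7/1.4/0.7 cancers at a true sensitivity of 60/80/90%. Sensitivity reads too high under all four rules. NPV reads too high, too low or is undefined.

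Specificity is also unverified, but changes little if unverified negatives are taken as benign. PPV for cancer can be estimated, although no reference is named for it: the hysterectomy specimen is described as examined for depth of invasion. Hyperplasia is part of objective 1 in Section 2, yet no section describes how it would be verified.

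The identification problem does not depend on the assumed numbers; their size does. The conclusion is confined to the visible text and would change if Appendix 1 shows a reference step for adequate benign results.

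**What to change.** Reconcile primary outcome 1 with the pathway in Section 3.1 Main study.

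1. Limit outcome 1 to what the pathway supports: diagnostic yield among all attempted ultrasound-guided biopsies, with failed and inadequate samples in the denominator and an exact interval, plus PPV for cancer with hysterectomy histology named as the reference.
2. Report sensitivity and NPV for cancer only against a predefined reference covering every biopsied woman: later or surgical histology where it exists, otherwise a records or registry check over a fixed window whose length is stated. Define inadequate and its scoring in advance. Add consent for the check and state that the linkage key implied by coded labels is kept, since the protocol also says patients are anonymised. State that this reference is imperfect and differs between women, and that the interval will be wide (8/8: 63-100%; 4/4: 40-100%).
3. Make no sensitivity or NPV claim for hyperplasia, because a records check cannot find hyperplasia that was missed and never re-sampled; report the number detected. Make no paired accuracy claim against hysteroscopy.

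The cost is protocol wording, a consent line, follow-up and end-of-trial definitions extended to these women, a records check on at most about 80 women, and probably an ethics amendment. The primary claim becomes more modest, and sensitivity stays imprecise even after the check. No extra procedure or change in clinical management is needed.

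Minimum version: define the reference standard and the scoring of inadequate and unverified results, and drop the sensitivity and NPV claims.
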